stimulation (cTBS) did not find group-level clinically meaningful change, although an extended dose (total of 6 weeks daily) did improve outcomes with 1Hz.³⁶ Importantly, in the only study measuring neural correlates of treatment, Wu et al.³³ detected significant decreases in activation of SMA and functionally connected CSTC nodes (i.e., bilateral M1) after only a 2 day course of cTBS, leading to continued interest in using TMS to alter tic-related neural pathology.

Our recent research suggests rTMS improves tic suppression ability more robustly than it reduces baseline tic frequencies. PI [name] measured acute effects of 1 Hz vs. sham rTMS over SMA using the TST (K23MH103617; for detail see "Preliminary Data" below) and found that active 1Hz rTMS enhances tic suppression ability. Notably, reduction in tic frequency was more robust in conditions measuring tic suppression ability compared to a "free to tic" baseline. These data suggest that inhibitory stimulation of SMA with rTMS may benefit those with tics by enhancing their capacity to voluntarily inhibit tics.

2.3. Existing Literature: Taken together, the existing literature and our preliminary data suggest that augmenting CBIT with inhibitory stimulation of SMA using TMS may boost tic suppression ability, which in turn may increase the efficacy of CBIT. This synergistic approach aligns with converging evidence suggesting that combining brain stimulation with targeted therapy is a potentially powerful approach for treating neuropsychiatric disorders.³⁷

3. Study Endpoints/Events/Outcomes

- 3.1. Primary Endpoint/Event/Outcome:
 - 1) Neural target engagement: Within-subject change in resting state fMRI connectivity of SMA-mediated brain circuits.
 - 2) Behavioral target engagement: Within subject change in tic suppression ability as measured by the Tic Suppression Task (TST).
- 3.2. Secondary Endpoint(s)/Event(s)/Outcome(s):
 - 1) Two TMS procedures, both intended to inhibit activity in SMA, will be compared using data from our safety and feasibility measures.
 - 2) Between group differences on secondary measures of clinical and neural function.

4. Study Intervention(s)/Investigational Agent(s)

4.1. Description: All participants will receive 10 daily sessions of CBIT, a wellestablished behavioral treatment that is considered by the American

PROTOCOL TITLE: Transcranial Magnetic Stimulation to Augment Behavior Therapy for Tics VERSION DATE: 2/24/2022

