Academy of Neurology to be the first-line intervention for tics.⁶ Immediately prior to each CBIT session, participants will undergo TMS targeting the SMA. The specific type of TMS procedure will be randomly assigned between subjects and be either: 1 Hz repetitive TMS (rTMS), continuous theta burst stimulation (cTBS), or sham stimulation.

4.2. Drug/Device Handling:

TMS device. Stimulation will be delivered using a Magstim Super Rapid2 stimulator (Magstim Company Ltd, UK). The device will be used to deliver electromagnetic stimulation through a small coil positioned over a targeted area on the scalp. The manufacturer's indication for use is to stimulate peripheral nerves and the human cortex for diagnostic and research purposes.

We will use a Magstim air-cooled 70mm figure-eight coil for motor threshold determination and active TMS conditions. Sham stimulation will use the Magstim sham air-cooled coil, which produces auditory signals identical to an active coil but contains a mu-metal shield that diverts the majority of the magnetic flux such that a minimal (<3%) magnetic field is delivered to the cortex.

The device is installed and set-up at the University of Minnesota Non-Invasive Neuromodulation Laboratory (NINL). The device will only be able to be administered by trained personnel. The device is located in a locked, access controlled room.

[figure not shown]
Operation of the TMS device (MAGSTIM Super Rapid 2) will follow the procedures outlined in the attached "Operating Manual."

- 4.3. Biosafety: N/A
- 4.4. Stem Cells: N/A
- 4.5. Fetal Tissue: N/A

5. Procedures Involved

5.1. **Study Design**: The study is a double-blinded randomized control trial that will examine whether combining Comprehensive Behavioral Intervention for Tics (CBIT) with inhibition of the

PROTOCOL TITLE: Transcranial Magnetic Stimulation to Augment Behavior Therapy for Tics VERSION DATE: 2/24/2022

supplementary motor area (SMA) using transcranial magnetic stimulation (TMS) normalizes activity in the SMA-connected circuits, improves tic suppression ability, and enhances CBIT outcomes in young people with tic disorder. We will compare two rTMS procedures, 1 Hz rTMS and continuous theta burst stimulation (cTBS), against sham stimulation. Youth with chronic tics (n = 60) will complete 10 daily sessions of CBIT plus randomly assigned TMS procedure, with fMRI, behavioral, and clinical assessments before and after treatment and at 1 and 3 month follow-ups (figure 1).

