• Aim 1. Target engagement: Brain. 1) Primary measure of neural target engagement will be decreased activation in SMA. Hypothesis 1: Either or both active TMS groups will demonstrate within-subject decrease (effect size $\eta 2=0.18$ in an ANOVA) in SMA activation post-treatment, as measured with an fMRI finger tapping task. While this is a large effect size in practice, we point out that Wu et al (2014) observed a much larger effect size of η 2=0.41 in the decrease in SMA activity comparing active vs sham cTBS. 2) Secondary measure of neural target engagement will be change in fMRI resting state functional connectivity of at least one SMA-mediated circuit (SMA-DLS, SMA-M1). Hypothesis 2: Either or both active TMS groups will demonstrate within-subject change (effect size $\eta 2=0.18$ in an ANOVA) in resting state fMRI connectivity (RSFC) of at least one SMA-mediated circuit (SMA-DLS, SMA-M1) post-treatment. A region of interest (ROI) analysis will be performed to determine the time*treatment group differences in SMA activation elicited by an fMRI motor task (finger tapping). The SMA ROI will be identified by placing a seed (sphere with 5mm radius) that matches the coordinate used for individual TMS coil placement. Activation parameters in the SMA will be identified in a first-level analysis, using a general linear model (GLM) to model each subject's SMA time course during the motor task. These activation parameters will be used in a subsequent linear mixed effects (LME) model. The predictors of the LME will include the baseline activation, group indicators for

PROTOCOL TITLE: Transcranial Magnetic Stimulation to Augment Behavior Therapy for Tics VERSION DATE: 2/24/2022

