the stimulation groups, and baseline x group interactions. Random effects will be used to model within-subject variation from the first-level analyses. Altogether, the LME will allow us to model how the within-subject change in activation from pre-treatment to post-treatment differs across active and sham conditions. *In addition*, we will also investigate the effects of each TMS regimen on the connectivity in the entire CSTC. To this end, we will extract the ROI-level time courses from each region in the CSTC, and we will use partial correlations to obtain an estimate of connectivity between each ROI pair within the CSTC while accounting for the data observed in the other ROIs. Given the collection of partial correlations for each study participant, we will use the SPU test, which uses the collection of partial correlations simultaneously, to assess for group differences across the sham and TMS regimens.⁷⁵

- Aim 2. Target engagement: Behavior. Hypothesis: Either or both active TMS groups will show within-subject improvement (small effect size of at least Cohen's d = 0.3) in tic suppression ability as measured by the Tic Suppression Task (TST). TST "tic suppression ability" scores will serve as the primary outcome in an ANOVA model. An ANOVA will be used to establish if there exist differences in how the 1Hz, cTBS, and sham conditions affect change in tic suppression ability from pre- to post-treatment. Group indicators for these conditions will be the primary predictors for the model.
- Aim 3. Assess dose-response relationship. Changes in brain (Aim 1) and behavior (Aim 2) targets will be compared between active TMS groups (1Hz rTMS vs. cTBS) using ANOVA. In the case that both active TMS regimens are found superior to sham, we will compare the regimens on safety and feasibility. We will use 2-sample t-tests to compare the two regimens using data from our safety and feasibility measures and prioritize the regimen with significantly better (p<.05) outcomes.
- 15.2. Power Analysis: In Aim 1, hypothesis 1 our proposed sample size after accounting for expected attrition will give us 80% power to detect an effect size of at least $\eta^2=0.18$ for differences in SMA activation between active TMS and sham. For Aim 2, our proposed sample size will give us 80% power to detect an effect size of at least d = 0.90 for a within-subject improvement in tic suppression ability. Our preliminary data showed effect sizes of this magnitude.

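### Section 3.1 and section 15.1 name different primary neural endpoints, neural power is given only for the one in 15.1, and nothing says which governs

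*Combined protocol and SAP*

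**What the plan says.** - **Section 3.1 (primary endpoint):** "Neural target engagement: Within-subject change in resting state fMRI connectivity of SMA-mediated brain circuits". Task activation does not appear. The other primary outcome is behavioural, on the Tic Suppression Task (TST).
- **Section 15.1, Aim 1:** "Primary measure of neural target engagement will be decreased activation in SMA", assessed with finger tapping in the scanner. It continues: "Secondary measure of neural target engagement will be change in fMRI resting state functional connectivity of at least one SMA-mediated circuit". The circuits are SMA-DLS and SMA-M1. Both hypotheses carry η²=0.18. The mixed model is written for activation, and its stated purpose is to show "how the within-subject change in activation from pre-treatment to post-treatment differs across active and sham conditions".
- **Section 15.2:** "In Aim 1, hypothesis 1 our proposed sample size after accounting for expected attrition will give us 80% power" for η²=0.18 in SMA activation. It also gives power for Aim 2 (TST, d=0.90). It gives none for connectivity.
- **Section 5.2 and Table 1:** the tapping task is described as serving coil placement and SMA localization. No outcome role is stated.
- **Section 5.1:** the trial is run "with fMRI, behavioral, and clinical assessments before and after treatment". Section 11.4 pays for two scans.

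**The concern.** A trial's primary endpoint should be identifiable from its own protocol. Here the two sections that define it reverse the ranks of the same two measures, and both statements stand in the current version. The revision history mentions no change of endpoint.

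If the two measures disagree at the end of the trial, 3.1 and 15.1 support different main neural conclusions from the same data. Until the sections match, the label could in principle be settled once both results are known. Nothing in the documents suggests that anyone intends this.

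**Working it through.** **Passages side by side**

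| Place | Resting-state connectivity | Finger-tapping SMA activation |
|---|---|---|
| 3.1 | Primary | Not mentioned |
| 15.1, Aim 1 | Secondary | Primary |
| 15.2 | No power statement | 80% power at η²=0.18 |
| 5.2 and Table 1 | Acquired; no rank given | Coil placement and localization only |

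Sections 15.1 and 15.2 agree with each other. Section 5.2 and Table 1 fit 3.1 better. A post-treatment tapping measurement is compatible with two scans, but the procedures do not describe it as an outcome.

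**Inputs**

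- From the documents: 60 enrolled, three arms, η²=0.18, 80% power after attrition.
- Assumed: alpha 0.05 (p<.05 is stated only for Aim 3); equal arms; one three-group F-test per measure; correlation between measures 0 to 0.5; 48 or 60 evaluable. The attrition rate is not stated.

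**Step 1: reproduce the plan's power.** In a one-way ANOVA with three groups, the noncentrality is λ = N × 0.18/0.82, with 2 and N−3 degrees of freedom.

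- N=47: λ = 10.32, power 79.98%.
- N=48: λ = 10.54, power 80.9%.
- N=60: λ = 13.17, power 89.6%.

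So 48 is the smallest number that reaches the stated 80%, which corresponds to 12/60 = 20% attrition. A single named circuit at the same η² has the same power.

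**Step 2: opposite verdicts when both measures truly change by η²=0.18.** For independent measures with power p, the chance that exactly one is significant is 2p(1−p).

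- N=48: 2 × 0.809 × 0.191 = 0.309.
- N=60: 2 × 0.896 × 0.104 = 0.186.

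Correlation lowers this. Simulation with correlation 0 to 0.5, with either one or both active arms differing from sham, gives about 22-31% at 48 and 14-19% at 60 for activation against one circuit. Against success on at least one of two circuits, it gives about 18-21% at 48 and 11% at 60.

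**Step 3: false positives if nothing changes and the label were settled after results.** For two independent tests at 0.05, the chance that at least one is significant is 1 − 0.95² = 0.0975. Simulation over correlation 0 to 0.5 gives about 9-10%, against 5% for one fixed endpoint. The same 9-10% applies to the at-least-one-circuit rule with two unadjusted tests.

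**Step 4: sensitivity to the decision rule.** Section 15.1 states effect sizes, not an alpha. Suppose success meant an observed η² of at least 0.18, with 48 evaluable. The threshold is F = (0.18/2)/(0.82/45) = 4.94.

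- The null pass rate is 1.2% per measure and 2.3% for either of two independent measures.
- When both true values are 0.18, each passes with probability 0.605, so they disagree in 2 × 0.605 × 0.395 = 48% of trials.

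The figures in Steps 2 and 3 therefore depend on the rule.

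**The case against.** **The label conflict may be only a slip in 3.1.** A reader might infer that activation was meant, because 15.1 specifies it in detail and 15.2 powers it. The documents do not establish this: Table 1 and 5.2 give the tapping task only a targeting role, which leans the other way. It would also be wrong to say that 15.2 powers activation alone, since it powers the TST too.

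**The magnitudes are not specific to this plan.** Any two independent endpoints with 81% power disagree in about 31% of trials, and the plan states no alpha for Aim 1. This stands. The figures show how often the conflict could matter under a conventional rule; they are not properties of the written plan.

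**A reader might want the three-group test to gate the active-versus-sham contrasts.** Both hypotheses allow success in one active arm ("Either or both active TMS groups will demonstrate within-subject decrease"; "Either or both active TMS groups will demonstrate within-subject change"), and no rule links the overall test to the contrasts. That is a separate trade-off, and resolving the label conflict does not require a gate. Counting only false claims of a decrease, the ungated rate is about 4.5%. At 48 evaluable, a gate would lower power for at least one active-versus-sham claim from 90% to 81% if both active arms work, and from 80% to 75% if one does.

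**Conclusion.** The contradiction holds and should be corrected. Sections 3.1 and 15.1 rank the two neural measures in opposite order, 15.2 gives neural power for activation only, and no passage reconciles them. This rests on the text alone, with no assumptions.

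The size is conditional. Opposite verdicts in about 22-31% of trials at 48 evaluable (14-19% at 60), and false positives of about 9-10% instead of 5%, hold under the alpha, equal arms, F-test rule and correlation range listed above. The stated 80% power is reproduced at 48 evaluable, so the problem is one of definition and not of arithmetic.

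The documents do not show which section is in error, and they give no evidence of an intention to choose the endpoint after seeing results.

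**What to change.** By dated amendment, before the study team examines outcome data by arm (routine monitoring-board review aside), name the same single primary neural endpoint in 3.1, 15.1 and 15.2, and label the other secondary.

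- **If SMA activation is chosen:** change 3.1, and state in Table 1 and 5.2 that the tapping task is also a pre- and post-treatment outcome. The existing model and power statement stand. The cost is wording only.
- **If connectivity is chosen:** change 15.1 and 15.2. Name one circuit, or apply Holm across SMA-DLS and SMA-M1. Write the analysis model, because the mixed model in 15.1 covers activation only and the connectivity analysis described there is a network-wide test. Add a power statement.

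One named circuit at η²=0.18 keeps 80.9% power at 48 evaluable. Under Holm at 48, power to show at least one circuit is 86-92% if both change by that amount, and about 72% if only one does.

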- 5.2. Study Procedures: Overall, study procedures include (a) pre-screening for eligibility determination, (b) four assessment sessions (pre-treatment, post-treatment, 1-month and 3-month follow ups), and (c) ten daily sessions of CBIT+TMS. Consent and assent will be obtained prior to the start of the pre-treatment assessment visit (figure 1).
 - Eligibility Assessment will occur prior to study enrollment. Parents/participants who contact study staff expressing interest in the study will be given a brief description of study procedures and asked to complete a phone or video chat (via Zoom) screen to determine preliminary eligibility. This screen is expected to take 25 minutes. Those potentially eligible will be asked to provide documentation of current medications. A signed release of information for medical record documents will be requested if necessary for eligibility determination.
 - **Optional detailed eligibility assessment:** In some cases, it is possible that phone screening outcome is unclear but could be clarified with an abbreviated version of the pretreatment assessment visit focused on the specific eligibility question (e.g., whether tics meet minimum severity threshold). In these cases, we will conduct a focused eligibility assessment via Zoom. Consent/assent will occur at this visit. Measures will be selected from the list of approved measures for the pre-treatment assessment (Table 2, column 1). This assessment is expected to take no more than 1 hour. For participants deemed eligible, we will carry-forward data when possible and accordingly shorten the next assessment visit to reduce participant burden.
 - **Optional accommodations:** In order to ease participant burden, parent-report and self-report measures can be completed outside of the assessment or follow-up visit. All surveys must be completed within the 5 days following the visit date.

PROTOCOL TITLE: Transcranial Magnetic Stimulation to Augment Behavior Therapy for Tics VERSION DATE: 2/24/2022

- Study Assessment Measures: Assessment procedures include a structured diagnostic interview, a clinician-administered rating scale for tic severity, parent-report and self-report measures for tic symptoms and other related emotional symptoms, and safety screening for MRI and TMS. Specific measures and the timing of administration are below in Table 1.

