 - Timing: Consent/assent will be obtained at the first point of formal assessment (optional detailed eligibility assessment or pre-treatment assessment visit) (Step 2). Daily sessions of CBIT+TMS (Step 4) will begin within 10 calendar days of the pre-treatment assessment. Participants will complete 10 CBIT+TMS visits within 13 business days. The post-treatment visit will be completed within the 10 calendar days following the last CBIT+TMS visit. The 1-month assessment will be completed 4-6 weeks after the last CBIT+TMS visit, and the 3-month assessment will be completed 12-14 weeks after the last CBIT+TMS visit.

Table 1. Study measures		Steps in Fig 1		Time (min)			
	Steps in flow chart (Figure 1)	1	2	4	5	6,7	
MEASURE	DETAILS						
Phone Screening	Eligibility, TMS safety screen ^{38,39}	x	x				20
Medical records	Last doctor visit, current medications, relevant/available documents; used for eligibility determination	х					
MRI safety screen	Eligibility	x	x		x		5
Demographics	Sample characteristics		x				10
IQ	Eligibility		x				15
MINI 7 KID ⁴⁰ or adult ⁴¹	Structured diagnostic interview		x				30

PROTOCOL TITLE: Transcranial Magnetic Stimulation to Augment Behavior Therapy for Tics
VERSION DATE: 2/24/2022

Yale Global Tic Severity Scale, YGTSS ⁴²	Gold-standard, clinician-administered tic severity scale. Includes symptom checklist of specific tic types.	x		x	x	30
Tic Suppression Task ^{12,43}	Direct observation measure of tic suppression ability	x	x	x	×	10
Parent/Adult Tic Questionnaire ^{44,45}	Adult-self or parent-report measure of tic symptoms and severity	x		x	x	5
Premonitory Urge for Tics Scale ^{46,47}	Self-report measure of intensity of urges to tic	x		x	x	5
Child/Adult Behavior Checklist ^{48,49}	Parent- or adult-self report measuring broad emotional and behavioral functioning	x		x	x	15
Sheehan Disability Scale ⁵⁰	Self- and parent measure of functional impairment	x		x	x	10
Tic Impact questions	Self- and parent-rated measures of how tics impact daily function	x		x	x	5
Behavior Rating Inventory of Executive Function ⁵¹	Self- and parent-rated measure of impairment of executive function	x		x	x	15
Ask Suicide-Screening Questions (ASQ)	Clinician-administered screen of suicidality	х		x	x	5
TMS Adverse Effects Questionnaire ³⁹	Tracks side effects of TMS		x	x	x	5
Clinical Global Impressions (CGI)	Clinician, patient, parent-rated global measure of illness severity and improvement	x		x	x	2

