 - Sham: to enhance blinding, half of sham participants will be exposed to the 1 Hz sequence and half will be exposed to the cTBS sequence
 - Number of sessions: 10 day sessions, delivered daily on weekdays
 - Immediately after the stimulation ends, the participant will be transitioned to a private room for the CBIT session. The *TMS Adverse Effects Questionnaire³⁹* will be completed by the participant and TMS operator at the end of each study visit.
 - rTMS sessions will be video recorded to later be coded for tic occurrences.
- Blinding procedures will be implemented to control for expectancy effects related to TMS stimulation. Persons who will be blind to TMS status are: participants; parents (if applicable); study staff administering clinical assessments, coding TST videos, delivering CBIT therapy, and collecting the MRI data; and all study investigators except Drs. [name] and [name]. Unblinded personnel will be [name], the study statistician and person responsible for randomization scheme oversight; [name], TMS operator supervisor; and the TMS operator. Staff who administer clinical rating scales and code TST videos will not be present for a given participant's CBIT+TMS visits to also ensure blinding to overall therapy progress. Staff will be trained and supervised on assessment scales by [name], who will audit YGTSS administrations for inter-rater reliability. Staff will be trained in TST coding by [name], who will code a set of video clips to monitor inter-rater reliability. For each of these measures (YGTSS

PROTOCOL TITLE: Transcranial Magnetic Stimulation to Augment Behavior Therapy for Tics VERSION DATE: 2/24/2022

and TST), the supervisor will audit 100% of the first ¹/₃ of the initial visits, 50% of the second ¹/₃ of participants, and 20% of the third ¹/₃ of the participants for inter-rater reliability. Forms assessing blinding adequacy will be given to participants, parents, and blinded staff who conduct CBIT sessions and assessments visits at post-treatment.

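### The five-day allowance for questionnaires includes the pre-treatment visit and can overlap the start of daily treatment, so the timing rules in section 5.2 need reconciling

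*Combined protocol and SAP*

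**What the plan says.** Section 5.2 (Optional accommodations) states that "parent-report and self-report measures can be completed outside of the assessment or follow-up visit". The only time limit attached is "All surveys must be completed within the 5 days following the visit date". The pre-treatment visit is one of the four assessment sessions listed in 5.2, and it is not excepted.

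Section 5.2 (Timing) fixes when treatment starts: "Daily sessions of CBIT+TMS (Step 4) will begin within 10 calendar days of the pre-treatment assessment". That is an upper limit only. The TMS parameters in 5.2 give the frequency as "10 day sessions, delivered daily on weekdays".

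Two other places point the opposite way. The design statement in 5.1 puts clinical assessments before treatment, and 5.2 (Randomization) puts allocation after the pre-treatment assessments. Neither mentions a form returned later under the accommodation.

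On the optional detailed eligibility assessment, a consented Zoom visit used when the phone screen is unclear, 5.2 adds: "For participants deemed eligible, we will carry-forward data when possible and accordingly shorten the next assessment visit to reduce participant burden". No maximum age is given for those data.

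**The concern.** A baseline form completed after several sessions can already contain some response to treatment. Every participant receives CBIT, so a late form in any arm would tend to shrink the measured within-arm change. If TMS also acts early, late forms in the active arms would absorb part of the difference from sham. Early action is plausible on the protocol's own account: section 2.2 cites reduced SMA activation after a two-day cTBS course and better tic suppression acutely after 1 Hz rTMS.

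The measures exposed are the parent- and self-report scales in Table 1: the Parent/Adult Tic Questionnaire, the Premonitory Urge for Tics Scale, the Behavior Checklist, the Sheehan scale, the Tic Impact questions and the BRIEF. They fall under the secondary clinical comparisons in 3.2. Those comparisons matter because the stated purpose includes better CBIT outcomes, whereas the primary endpoints in 3.1 are target engagement. A late baseline cannot be recovered afterwards.

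The carry-forward rule raises a separate question. The example given for the Zoom assessment is whether tics reach the severity threshold, so the YGTSS is the natural score to be carried. A score kept because it passed a threshold is open to regression to the mean, and it may be out of date when treatment starts.

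**Working it through.** The plan gives no figure to reproduce, so the check sets the windows against each other.

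**Inputs, all from 5.2.** The form deadline is visit day + 5, with calendar or business days not stated. The first session may fall up to visit day + 10 calendar days, with no minimum. Sessions run once per weekday, 10 in all.

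**Formula.** Sessions at risk = number of weekdays d with first session ≤ d ≤ form deadline. A session on the deadline day is counted, because a form returned later that day would still comply.

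**Worked case.** Visit on Monday (day 0), first session on Tuesday, deadline on Saturday (day 5). Tuesday to Friday gives 4 sessions. For a Friday visit with a Monday start (day 3), the deadline is Wednesday, so Monday to Wednesday gives 3.

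| First session | Calendar-day reading | Business-day reading |
|---|---|---|
| Next weekday, Monday visit | 4 | 5 |
| Next weekday, Tuesday to Friday visit | 3 | 5 |
| Day 5 | 1 | 3 |
| Day 6 | 0 | 2 |
| Day 7 | 0 | 1 |
| Days 8 to 10 | 0 | 0 |

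The overlap therefore closes from day 6 on the calendar-day reading and from day 8 on the business-day reading.

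**Does anything else force the forms in first?** Stratification uses only TST performance and medication status (5.2, Randomization). The entry criteria in 8.1 and 8.2 do not name these questionnaires. Section 5.3 lets the pre-treatment visit be split over two dates up to a week apart, so the date from which the five days run is itself undefined.

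**Is the rule harmful at later visits?** No. The post-treatment visit is within 10 days of the last session, so its forms arrive by day 10 + 5 = 15 (calendar days). The 1-month window opens at 4 weeks = 28 days, so the two do not collide.

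**Is the age of carried-forward data limited indirectly?** Section 5.3 gives a total of up to 20 weeks = 140 days. The maximum windows are 10 days to the first session, 18 calendar days as the longest span of 13 business days, and 14 weeks = 98 days to the last follow-up: 10 + 18 + 98 = 126. That leaves 140 − 126 = 14 days. With a next-day start, the shortest span of 10 weekdays (11 days) and the 12-week follow-up, the sum is 1 + 11 + 84 = 96, leaving 44 days. Either limit applies only if the 20 weeks are counted from the Zoom assessment, which 5.3 does not say. By contrast, 5.2 does set an age limit for a prior IQ test (24 months).

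**The case against.** The strongest reply is that the questionnaires are pre-treatment assessments, so 5.1 and the randomisation rule already require them before allocation and hence before treatment. A reader might otherwise infer that some baselines will be post-treatment, and the documents do not support that. What stands is narrower. The general statements show intent, the specific rule on late forms permits something else, and nothing says which prevails.

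A next-weekday start is also unlikely. Before session 1 the team needs confirmed eligibility, an MRI, an individual activation map and electric-field model, a TST result for stratification, and medical review. That makes the 3-to-4-session case an outer limit rather than the usual course. It does not remove the overlap, because a start by day 5 is enough.

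Four stronger readings are tempting but unsupported:

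- **A numerical bias.** Four of ten sessions is 40% of treatment, and one could multiply that by an assumed share of late families. The documents give no such share, no questionnaire variance and no response curve. Linear benefit also fits poorly with 5.2, where session 1 is psychoeducation and competing response training starts at session 2.
- **A contaminated baseline covariate.** Section 15.1 specifies no model with a questionnaire baseline as covariate. Its only baseline outcome covariate is SMA activation.
- **Regression to the mean biasing the comparison of arms.** It acts on all randomised arms alike. It can inflate within-arm change and add noise, but does not by itself favour an arm.
- **Phone-screen scores used as baseline.** Carry-forward covers only the consented Zoom assessment. The text does not say that a YGTSS or TST will be carried, though it excludes neither. Since Timing labels both assessments Step 2, the 10-day limit could be read as running from either.

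**Conclusion.** The point holds as an unreconciled timing rule. As written, a baseline questionnaire can comply with its deadline and still follow up to 3 or 4 sessions (calendar days) or 5 (business days), given a start on the next weekday. The exposure falls to zero with a start on day 6 or later on the calendar-day reading, or day 8 or later on the business-day reading. It is confined to secondary parent- and self-report measures; the allowance does not reach fMRI, the TST or the clinician-rated YGTSS. How often it would happen, and how much bias would follow, cannot be computed from the documents.

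The missing age limit on carried-forward scores is a lesser point. It concerns a few borderline entrants and bears mainly on within-arm change and precision. Correction is still worthwhile, because an explicit rule permits an error that cannot be repaired later and prevention is cheap.

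**What to change.** In 5.2 (Optional accommodations), require pre-treatment surveys within 5 days of the visit and before both randomisation and the first CBIT+TMS session, so that the earliest of these limits governs. Keep the plain five-day rule for post-treatment and follow-up visits. State whether the days are calendar or business days and, for split visits, which date counts. Add a REDCap check of survey completion date against randomisation and first-session dates. This brings the accommodation into line with 5.1 and with 5.2 (Randomization).

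In the eligibility paragraph of 5.2, require that any change outcome carried forward, such as the YGTSS, falls within the same 10-day window before session 1, and otherwise is repeated.

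The cost is a few sentences, the date check, a reminder call for late forms, and about 30 minutes (the Table 1 time for the YGTSS) for the few participants who need a repeat. With the first change in place, no session can precede a compliant baseline survey.
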